#### Treatment of ETF, LCF or LPF:

Subjects meeting the criteria for either ETF, LCF or LPF will receive treatment with appropriate rescue medication, as determined by each individual site, and will be followed up for safety assessment until day 42, or until resolution of the malaria episode if this persists for longer than day 42.

#### 6.3.5. Clearance times (PCT and FCT)

Subjects will also be assessed for these secondary endpoints against the following definitions:

- **PCT**: Time needed to clear asexual parasite forms from the blood, parasite numbers fall below the limit of detection in a thick blood smear and remain undetectable for at least 48 hours.
- **FCT:** Time from the first dose of treatment to the time when body temperature falls to normal and remains so for at least 48 hours.

#### 6.4. Urine testing for antimalarial drugs

A urine sample will be taken for all subjects to test for the presence of chloroquine.

## 6.5. Pharmacokinetics

Up to five blood samples for population PK analysis will be collected from each subject. These samples will be collected within varying time windows:

- 1. 0.25-0.5 h
- 2. 1-3 h
- 3. 4-8 h
- 4. 12-24 h
- 5. Day 7

Samples 1-4 can be taken after any of the morning doses on Days 0-2. The fifth sample can be taken any time on Day 7. Sampling times within a particular window should be spread across that window among subjects rather than being grouped at extreme ends of the window (e.g. 8-24 h window – not all samples be taken at 8 h or 24 h). The dates and exact times of sampling, as well as the dates and exact times of drug administration must be recorded in the eCRF.

#### Method for handling PK blood samples

Blood, approximately 2mL, will be collected into polypropylene tubes containing lithium heparin, mixed gently and placed on crushed wet-ice for no longer than 30mins, until centrifugation at 1800g for 10 minutes using a refrigerated centrifuge. The resultant plasma will be separated, and transferred in equal volumes to two uniquely labelled clear polypropylene tubes and frozen immediately over solid carbon dioxide or in a freezer at nominal –80°C. Samples will be transported frozen to WW Bioanalysis, DMPK, Ware, to be stored at approximately -80°C until analysed. Plasma concentrations of CPG, CCP, DDS, ART and DHA will be determined using currently approved methods by the WW Bioanalysis group, Ware and be used to evaluate the population pharmacokinetics of these compounds, if data permit.

# 7. INVESTIGATIONAL PRODUCT(S)

# 7.1. Description of Investigational Product

Chloroproguanil/Dapsone/Artesunate Tablets (CDA Tablets) are available as brown or yellow, peanut shaped, film-coated tablets. These contain either 12/15/24 mg or 60/75/120 chlorproguanil (as the hydrochloride)/Dapsone/Artesunate respectively. Matching placebo tablets to both tablets strengths are also available.

Artemether /lumefantrine Tablets are available as pale yellow uncoated tablet. These tablets will be coloured film-coated to differentiate them from the commercial product These contain 20/120 mg Arthemether/Lumefantrine respectively. Matching placebo tablets are also available.

#### 7.2. Dosage and Administration

Target doses of CPG, DDS and artesunate will be 2, 2.5 and 4 mg/kg/day respectively. Treatment will be administered once daily for 3 days, dosed according to weight. CDA tablets will contain a break-line and are intended to be broken in half in some weight bands to facilitate dosing. See Appendix 1 for dosing schedule.

Artemether-lumefantrine will be given as a 6-dose course, administered twice daily for 3 days, with the second dose administered 8 hours after the initial dose. Artemether-lumefantrine is also dosed according to weight (See Appendix 1 for dosing schedule). Artemether-lumefantrine is recommended to be administered with breast milk, or condensed milk in children, therefore both treatment groups will receive their study medication in this manner.

Breast milk or at least 5ml condensed milk should be given at least 30 mins prior to administration of study drug.

Younger children may receive their tablets crushed and mixed with water just prior to administration for both treatment groups. It is intended to record whether tablets are crushed in the electronic case report form (eCRF).

Subjects who vomit any dose of study medication within the first 30mins after dosing will be re-dosed. Subjects who vomit the second dose within the next 30mins will be given appropriate rescue medication and should remain in the study for safety assessment until day 42.

## 7.3. Dose Rationale

The target doses of CPG and DDS are equivalent to the marketed product LAPDAP, 2mg/kg/day CPG, 2.5mg/kg/day DDS. The artesunate dose to combine with CPG and DDS was determined from a dose-ranging study (SB-714703/003); 4 mg/kg/day, as discussed in the Introduction and Investigator's Brochure.

The 6-dose course for artemether-lumefantrine was chosen as this has been shown to be superior to the 4-dose course and it is anticipated that the 6-dose course will be in mainstream use in SSA by the time CDA is projected to be available on the market. Comparing CDA to the 4-dose course would be open to criticism that we were comparing our drug against an inferior product.

## 7.4. Blinding

CDA tablets and matching placebo, as well as commercial Coartem (artemetherlumefantrine) tablets and matching placebo (colour film-coated to differentiate the active and placebo tablets from the commercial product) will be used in the study.

Treatment allocation will be assigned via the Registration and Medical Ordering System (RAMOS).

#### CONFIDENTIAL

**Only in the case of an emergency,** when knowledge of the investigational product is essential for the clinical management or welfare of the subject, the investigator may unblind a subject's treatment assignment. The investigator will, whenever possible, discuss options with the Medical Monitor, on-call physician, or appropriate GSK study personnel before unblinding. If the blind is broken for any reason and the investigator is unable to contact GSK prior to unblinding, the investigator must notify GSK **as soon as possible following** the unblinding incident **without revealing the subject's study treatment assignment,** unless the information is important to the safety of subjects remaining in the study. In addition, the investigator will record the date and reason for revealing the blinded treatment assignment for that subject in the appropriate data collection tool (as defined in Section 12.7).

If the treatment blind needs to be broken for an individual subject during the study, as a result of a medical emergency, it will be done by placing a call to RAMOS to break the blind. Further details will be provided in the study reference manual. If the blind is broken for a subject, they should remain in the study for safety assessment, but will be ineligible for the per-protocol population.

If a serious adverse event (SAE; as defined in Section 10.2, "Definition of an SAE") is reported to GSK, Global Clinical Safety and Pharmacovigilance (GCSP) staff may unblind the treatment assignment for the individual subject. If an expedited regulatory report to one or more regulatory agencies is required, the report will identify the subject's treatment assignment. When applicable, a copy of the regulatory report may be sent to investigators in accordance with relevant regulations, GSK policy, or both.

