#### 7.11. Treatment of Investigational Product Overdose

#### CDA

Since chlorproguanil/dapsone has been shown to induce methaemoglobinaemia in clinical trials, clinically significant levels may be encountered in overdose. In addition to the undesirable effects seen with the recommended doses described in the DCSI [Investigator's Brochure GlaxoSmithKline Document Number GM2002/00293/01], (Section 6), the following additional events have been reported in association with dapsone or proguanil. Chlorproguanil is a dihalogenated congener of proguanil; undesirable effects associated with proguanil overdose were used in the absence of available chlorproguanil data. Coma, anxiety, mental disturbance, restlessness, hyperexcitability followed by depression, spasms or convulsions, hypotonia, hyporeflexia and ataxia, cyanosis, anuria and haematuria, sweating, fever, acute renal failure, permanent retinal damage, blindness, motor neuropathy, renal irritation and epigastric discomfort.

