- g. Haemoglobin values: a drop of  $\geq 40\%$  of baseline haemoglobin and / or all blood transfusions, and/or all haemoglobin values of < 5g/dL
- h. Methaemoglobin values: all values of  $\geq 20\%$ , and /or values of  $\geq 10\%$  but <20% with associated clinical symptoms of methaemoglobinaemia.

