# Per-protocol populations (PP)

The Per Protocol (PP) population will consist of all subjects in the ITT population not identified as major protocol violators. The major protocol violations for which patients would be excluded from the PP population will be described in the Reporting and Analysis Plan and will represent violations that may impact the efficacy endpoints for

which non-inferiority comparisons are being made. The decision to exclude a subject from the PP population will be made prior to breaking the blind. This population will be used for primary analysis of the day 28 cure rate and supportive analysis of the secondary efficacy endpoints,

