# 11.3.5.7. Efficacy Analyses

The primary analysis is the Per Protocol analysis of the Parasitolgical Cure Rate (PCR-corrected) at Day 28.

A key supportive analysis will be the Intent-to-Treat analysis of the Parasitological Cure Rate (PCR-corrected) at Day 28, with missing data imputed as treatment failure

Additional sensitivity analyses of the primary endpoint will be performed to assess the robustness of the primary analysis to modifications in assumptions and methods. Analyses such as the following will be performed:

- Intent-to-Treat analysis of the Parasitological Cure Rate (PCR-corrected) at Day 28, with missing data excluded.
- Per Protocol analysis of the Parasitological Cure Rate (without PCR correction) at Day 28.

Secondary Analyses will include:

- Parasitological cure rate of CDA vs artemether-lumefantrine at day 14 (PCR corrected).
- Parasitological cure rate of CDA vs artemether-lumefantrine at day 42 (PCR corrected).
- Adequate Clinical and Parasitological Response rate (ACPR [World Health Organisation, 2003]) at day 14, 28 and 42 (all PCR corrected).
- Asexual parasite densities over time for CDA vs. artemether-lumefantrine.
- PCT of CDA vs artemether-lumefantrine.

- Gametocyte density over time of CDA vs artemether-lumefantrine.
- FCT of CDA vs artemether-lumefantrine.

Details of theses analyses will be documented in the Reporting and Analysis Plan (RAP).

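### Section 7.4 drops emergency-unblinded subjects from the primary per-protocol population even when they had already failed treatment, so a few failures can leave the non-inferiority test

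*Protocol*

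**What the plan says.** Protocol section 7.4 allows the investigator to break the blind only in an emergency, "when knowledge of the investigational product is essential for the clinical management or welfare of the subject, the investigator may unblind". The paragraph on emergency code-breaks through RAMOS ends with the consequence: such subjects are kept, but "they should remain in the study for safety assessment, but will be ineligible for the per-protocol population". It draws no distinction by timing, by reason, or by whether the outcome was already settled.

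The next paragraph of 7.4 gives a second route. After a reported SAE, "Global Clinical Safety and Pharmacovigilance (GCSP) staff may unblind the treatment assignment for the individual subject". That paragraph says nothing about per-protocol eligibility.

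Section 11.3.5.7 states: "The primary analysis is the Per Protocol analysis of the Parasitolgical Cure Rate (PCR-corrected) at Day 28". Sections 11.1 and 11.3.3.1 apply the -7% rule to the lower bound of the two-sided 95% confidence interval. Section 11.3.1 defines the per-protocol set as the ITT population without major violators. It leaves the list of violations to the Reporting and Analysis Plan, with the principle that they "will represent violations that may impact the efficacy endpoints". The ITT analysis, with a missing Day 28 assessment counted as failure, is a key supportive analysis.

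**The concern.** Exclusion from the primary population depends on an event after randomisation, and that event can be the endpoint itself. Section 6.3.4 counts danger signs or severe malaria with parasitaemia as early or late clinical failure. A child whose original infection returns as severe malaria is a failure on the Day 28 endpoint. If the site breaks the blind to manage that child, section 7.4 removes the child from the primary analysis. Nothing elsewhere in the current text puts such a child back.

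The rule also sits awkwardly with the principle in section 11.3.1. A code-break made as 7.4 permits is hard to call a protocol violation, and it cannot alter a slide or PCR result from a sample already taken.

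In a non-inferiority comparison, removing failures from the test arm narrows a real deficit and makes a false claim of non-inferiority more likely.

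**Working it through.** **Inputs from the protocol.** Evaluable subjects: 650 CDA and 325 artemether-lumefantrine (5.1, 11.2.2). Margin: 7 points. One-sided level: 2.5%. Planned cure rates: 93% and 95% (11.2.2).

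**Assumption.** The protocol gives no unblinding rate, so the number of failures removed, k, is varied.

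**Plan's own figure first.** With the unpooled standard error, SE = √[p₁(1−p₁)/n₁ + p₂(1−p₂)/n₂], and power = Φ[(0.07 − (p₂−p₁))/SE − 1.96]. At 93% and 95%, SE = 0.01569, so power = Φ(0.05/0.01569 − 1.96) = 89.0%. With the variance restricted to the −7% null (Farrington–Manning) it is 90.2%. The same method gives 90.6% at 605/650 against 309/325, which matches Table 1. The stated power of at least 90% is reproduced and is not in dispute.

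**One-sided error on the margin boundary.** Take true rates of 88% and 95%, so the CDA arm expects 650 × 0.88 = 572 cures and 78 failures. Removing k CDA failures gives n₁ = 650 − k and p₁ = 572/n₁. The chance of claiming non-inferiority is then Φ[(0.07 − (0.95 − p₁))/SE − 1.96].

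| CDA failures removed | Apparent difference (points) | SE | One-sided error |
|---|---|---|---|
| 0 | −7.00 | 0.01757 | 2.5% |
| 1 | −6.86 | 0.01753 | 3.0% |
| 2 | −6.73 | 0.01749 | 3.6% |
| 3.9 (5% of 78) | −6.47 | 0.01742 | 4.9% |
| 5 | −6.32 | 0.01737 | 5.9% |

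If 5% of failures are removed from each arm (3.9 CDA, 0.8 comparator), the error is 3.7%. At 10% of each arm it is 5.4%.

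**If the unblinded subjects are cures.** In the same model, removing 4 CDA cures gives 2.3% and removing 10 gives 1.9%. Removing 20 CDA subjects in the arm's own 88/12 mix leaves the error at 2.5%.

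**Effect on single results (lower bound = difference − 1.96 × SE).**

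| CDA | Comparator | Lower bound | Non-inferior? |
|---|---|---|---|
| 590/650 | 309/325 | −7.55% | No |
| 590/646 (4 failures dropped) | 309/325 | −6.95% | Yes |
| 605/650 (planned rate) | 309/325 | −5.06% | Yes |
| 605/645 (5 failures dropped) | 309/325 | −4.28% | Yes |

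A handful of exclusions can reverse a result that lies close to the margin. It does not alter one near the planned rates.

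**The case against.** **The failure route is narrow.** Section 6.3.4 gives early and late failures site-determined rescue medication and calls for no code-break. Children enter with uncomplicated malaria, are inpatients to Day 3 and are visited at home on Days 4 to 6. Only an emergency failure in which the site needs to know the allocation is affected. This stands, and it is why the expected number is small.

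**ITT keeps these subjects.** An unblinded recrudescence still counts as a failure in the key supportive analysis, so a divergence between the two populations would be visible. Section 7.4 already has the date and reason of investigator code-breaks recorded. This also stands, but the formal claim rests on the per-protocol result.

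**Excluding unblinded subjects is a recognised convention.** Later visits are no longer managed blind. That is a fair reason for a subject whose outcome is still open. It does not apply to one who has already failed.

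**A stronger reading that the text does not support.** A reader might infer that SAE-driven unblinding falls mainly on CDA and so favours it. The ingredients are there: "chlorproguanil/dapsone has been shown to induce methaemoglobinaemia in clinical trials" (7.11), and section 10.2 makes large haemoglobin falls, "all blood transfusions, and/or all haemoglobin values of" below 5 g/dL, and raised methaemoglobin reportable as SAEs. Two steps are missing. First, the ineligibility sentence belongs to the emergency paragraph and does not clearly reach the sponsor-safety route. Second, these events are not parasitological failures. Many of these children may be cures, and removing cures moves the error slightly down (1.9% to 2.3% above). The direction for safety-driven code-breaks is therefore not determined.

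**Conclusion.** The point holds in a limited form. Section 7.4 fixes an exclusion that can remove established failures from the primary test, and it is silent on whether unblinding by sponsor safety staff counts. The inflation, from 2.5% to about 3.0%, 3.6% or 4.9% for 1, 2 or about 4 CDA failures, rests on three assumptions: the true difference lies exactly on the margin, only CDA failures are removed, and the counts are illustrative because the protocol states none. At the planned rates the conclusion is unaffected. A reader might see this as a defect that invalidates the primary analysis. The narrow trigger and the retained ITT analysis do not support that. Severity is minor to moderate: a wording gap worth closing before unblinding.

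**What to change.** Amend section 7.4 as follows, and carry the change into the Reporting and Analysis Plan.

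- A code-break does not remove from the per-protocol population a subject who had met the failure definition at or before it. This includes a positive slide at that time that PCR later classes as recrudescence or as inconclusive. Such subjects count as failures.
- Unblinding by sponsor safety staff alone, with the site still blind, does not exclude a subject.
- All code-breaks are listed by arm, with date and reason.
- One sensitivity analysis includes every unblinded subject by the observed Day 28 slide and PCR result.

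The cost is a short amendment, one listing and one table. The downside is that a few subjects whose allocation was known to the site stay in the per-protocol population. Their failure was already established when the blind was broken. The change does not touch clinical management or the conditions for unblinding.

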## 7.5. Treatment Assignment

Subjects will be assigned to study treatment in accordance with the randomisation schedule. The randomisation schedule will utilise centre-based allocation.

The randomisation schedule will be generated by the Biomedical Data Sciences group at GSK, using Randall software. RAMOS will be used to allocate subjects to the treatment groups.

Once a randomisation number has been allocated to a subject, it cannot be re-assigned to any other subject at the site.

## 7.6. Packaging and Labelling

The investigational products will be supplied as individual bottles containing sufficient tablets for the whole dosing period of the study, with two bottles being allocated per patient. One bottle will contain either CDA active or placebo (either 12:15:24 or 60:75:120 tablet size), and the other artemether-lumefantrine active or placebo. Each bottle will be labelled with the following information; drug product (including fill count), storage conditions and dosage directions.

The contents of the label will be in accordance with all applicable regulatory requirements.

## 7.7. Preparation

The only preparation that may be applicable to either treatment would be the crushing of the tablets prior to administration in younger children.

Tablets will be crushed in a pestle and mortar, mixed with a little water for immediate administration to the younger children.

# 7.8. Handling and Storage

Investigational product must be dispensed or administered according to procedures described herein. Only subjects enrolled in the study may receive investigational product, in accordance with all applicable regulatory requirements. Only authorized site staff may supply or administer investigational product. All investigational products must be stored in a secure area with access limited to the investigator and authorized site staff and under physical conditions that are consistent with investigational product-specific requirements.

Study drugs will be administered by the investigator, or an appropriately qualified designee.

Drugs will be kept in secure storage conditions, at a temperature of less than 30°C. Final disposition of unused investigational product will be either destroyed at site, if appropriate facilities are available, or will be returned to GSK or a third party contractor.

## 7.9. Product Accountability

The investigator, institution, or the head of the medical institution (where applicable) is responsible for investigational product accountability, reconciliation, and record maintenance. In accordance with all applicable regulatory requirements, the investigator or the head of the medical institution (where applicable), or designated site staff (e.g., storage manager, where applicable) must maintain investigational product accountability records throughout the course of the study. The responsible person(s) will document the amount of investigational product received from and returned to GSK (when applicable), the amount supplied and/or administered to and returned by subjects, if applicable.

Investigational product will be accounted for to the number of tablets per patient pack.

## 7.10. Assessment of Compliance

Compliance will be reported as adherence with treatment group allocated, and with the correct dosage for their weight. A patient will be considered to be non-compliant if they do not receive the complete 3-day treatment course of investigational product. If a subject vomits a dose of study drug, they will be considered compliant if they are redosed within 30mins, and do not vomit the re-dose.

#### 7.11. Treatment of Investigational Product Overdose

#### CDA

Since chlorproguanil/dapsone has been shown to induce methaemoglobinaemia in clinical trials, clinically significant levels may be encountered in overdose. In addition to the undesirable effects seen with the recommended doses described in the DCSI [Investigator's Brochure GlaxoSmithKline Document Number GM2002/00293/01], (Section 6), the following additional events have been reported in association with dapsone or proguanil. Chlorproguanil is a dihalogenated congener of proguanil; undesirable effects associated with proguanil overdose were used in the absence of available chlorproguanil data. Coma, anxiety, mental disturbance, restlessness, hyperexcitability followed by depression, spasms or convulsions, hypotonia, hyporeflexia and ataxia, cyanosis, anuria and haematuria, sweating, fever, acute renal failure, permanent retinal damage, blindness, motor neuropathy, renal irritation and epigastric discomfort.

#### Treatment

The following treatments have been reported in the management of dapsone overdosage. No data was available for proguanil and symptoms should be treated as they arise. In case of accidental over-dosage, immediate induction of emesis and/or gastric lavage is recommended. Activated charcoal administered orally may be useful in shortening the half life of dapsone and monoacetyldapsone. Intravenous fluids may be required to promote diuresis. Methaemoglobinaemia may be treated with intravenous methylene blue. Methylene blue may exacerbate dapsone-induced Heinz body haemolytic anaemia and should not be given to individuals with G6PD deficiency. Ascorbic acid administration (0.5-2g) may also be of value in treating methaemoglobinaemia in G6PD deficient patients. It should not normally be used alone due to its slow speed of action. Additional supportive therapy may include oxygen, exchange transfusion and packed cell administration.

